12.3.1.4 Analysis Methods

Acute effectiveness for each subject will be determined as described in section 12.3.2. In order for a subject to meet the acute procedural success criterion for the 6-month effectiveness endpoint, the subject must be an acute procedural success for their index and reablation procedure (if required). Ambulatory ECG monitor recordings will be completed at the baseline and 6-month post final Phased RF ablation visit. Ambulatory ECG recordings will be read and summarized by the Holter core laboratory. For the baseline and 6-month post-ablation procedure ambulatory ECG recording, the percentage of time in clinically significant AF (AF > 10 minutes) will be calculated as the total number of seconds in clinically significant AF divided by the total analyzable ambulatory ECG monitor recording time in seconds. The percent reduction from baseline will be calculated as the difference of the percentage of time in clinically significant AF between the baseline and 6-month post-ablation procedure visit divided by the percentage of clinically significant AF at baseline. Subjects with at least a 90% reduction in clinically significant AF will be considered successful for the ambulatory ECG component of 6-month effectiveness endpoint. Adjustments to all cardiovascular medications including antiarrhythmic drugs and dates of all DC Cardioversions will be captured on the case report forms.

Only those subjects that have a baseline and 6-month post-procedure 48-hour ambulatory ECG monitor data that are readable by the core lab or are missing ambulatory ECG data but were 6-month effectiveness failures based on other criteria at the time of the visit cutoff date will be included in the analysis of this

objective. Specifically, the denominator for the 6-month effectiveness rate will include all subjects that had at least one Phased RF ablation procedure where an investigational catheter was deployed into the left atrium and have baseline and 6-month ambulatory ECG monitor data available or do not have ambulatory ECG data available but were 6-month effectiveness failures based on other criteria. The numerator will include all subjects in the denominator that meet all four 6-month effectiveness conditions. A two-sided 95% exact confidence interval for 6-month effectiveness rate will be calculated.

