12.3.1.3 Definition of 6 Month effectiveness

6-Month effectiveness will be defined as:

- Acute procedural success, AND
- $\geq 90\%$ reduction in clinically significant AF/AFL by 48-hour ambulatory ECG monitor. Clinically significant AF/AFL is defined as; any AF/AFL episode lasting longer than 10 consecutive minutes in duration, AND
- Off amiodarone for at least 90 days and off all other class I and class III antiarrhythmic drugs for at least 60 days prior to the 6-month ambulatory ECG monitor, AND
- Free from DC cardioversion for AF for at least 60 days prior to the 6-month ambulatory ECG monitor

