12.3.1.5 Determination of subjects for analysis

Only those subjects that have completed both a baseline and 6-month 48 hour ambulatory ECG monitor or are 6-month effectiveness failures based on other criteria will be included in the main analysis cohort for this objective.

In the event that the recording duration of the ambulatory ECG monitor exceeds 48 hours (e.g. a 7 day ECG patch monitor is used), the AF burden will be computed by the core laboratory for the initial 48 hours only.

Likewise, in the event the ambulatory ECG monitor is less than 48 hours (e.g. due to inadequate ECG patch monitor fixation, subject compliance) the AF burden will be determined by the core laboratory based on the total usable or analyzable recording period. Subjects may be asked to repeat an ambulatory ECG monitoring session if less than 24 hours of analyzable monitoring time is obtained. Subjects with less than 24 hours of usable ambulatory ECG recording time will be considered missing in the analysis (unless they are 6-month effectiveness failures based on other criteria) and included in sensitivity analyses as described below.

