### 3.3.1.2 Definition of 6 Month Effectiveness

6-Month effectiveness will be defined as:

- Acute procedural success, AND
- $\geq 90\%$  reduction in clinically significant AF/atrial flutter (AFL) by 48-hour Holter. Clinically significant AF/AFL is defined as any AF/AFL episode lasting longer than 10 consecutive minutes in duration, AND
- Off amiodarone for at least 90 days and off all other class I and class III antiarrhythmic drugs for at least 60 days prior to the 6-month Holter, AND
- Free from direct current (DC) cardioversion for AF for at least 60 days prior to the 6-month Holter

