### 3.3.1.3 Analysis Methods

Acute effectiveness for each subject will be determined as described in section 3.3.2.2. In order for a subject to meet the acute procedural success criterion for the 6-month effectiveness endpoint, the subject must be an acute procedural success for their index and reablation procedure (if required). Holter recordings will be completed at the baseline and 6-month post final Phased RF ablation procedure. Holter recordings will be read and summarized by the Holter core laboratory. For the baseline and 6-month post-ablation procedure Holter recording, the percentage of time in clinically significant AF (AF > 10 minutes) will be calculated as the total number of seconds in clinically significant AF divided by the total Holter recording time in seconds. The percent reduction from baseline will be calculated as the difference of the percentage of time in clinically significant AF between the baseline and 6-month post-ablation procedure visit divided by the percentage of clinically significant AF at baseline. Subjects with at least a 90% reduction in clinically significant AF will be considered successful for the Holter component of 6-month effectiveness endpoint. Adjustments to all cardiovascular medications including antiarrhythmic drugs and dates of all DC cardioversions will be captured on the case report forms.

Only those subjects that have a baseline and 6-month post-procedure 48-hour Holter data that are readable by the core lab or are missing Holter data but were 6-month effectiveness failures based on other criteria at the time of the visit cutoff date will be included in the analysis of this objective. Specifically, the denominator for the 6-month effectiveness rate will include all subjects that had at least one Phased RF ablation procedure where an investigational catheter was deployed into the left atrium (i.e. placed in the left atrium and phased RF energy delivered) and have baseline and 6-month Holter data available or do not have Holter data available but were 6-month effectiveness failures based on other criteria. The numerator will include all subjects in the denominator that meet all four 6-month effectiveness conditions. A two-sided 95% exact confidence interval for 6-month effectiveness rate will be calculated.

[REDACTED]

[REDACTED]

[REDACTED]

[REDACTED]

[REDACTED]

[REDACTED]

[REDACTED]

[REDACTED]

[REDACTED]

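### The 6-month effectiveness ECG component is defined on AF/AFL but scored on AF alone, and the SAP divides by total rather than analyzable recording time (minor)

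*Protocol*

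**What the plan says.** **Definition.** Protocol 12.3.1.3 states "Clinically significant AF/AFL is defined as; any AF/AFL episode lasting longer than 10 consecutive minutes in duration", and SAP 3.3.1.2 says the same: "Clinically significant AF/AFL is defined as any AF/AFL episode lasting longer than 10 consecutive minutes in duration". The ECG component requires a reduction of at least 90% in that quantity.

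**Scoring.** Protocol 12.3.1.4 turns this into a burden: "the percentage of time in clinically significant AF (AF > 10 minutes) will be calculated as the total number of seconds" in that state, "divided by the total analyzable ambulatory ECG monitor recording time in seconds". The next sentence takes the percent reduction from baseline, again in AF. The pass rule follows: "Subjects with at least a 90% reduction in clinically significant AF will be considered successful for the ambulatory ECG component". SAP 3.3.1.3 has the same three steps, also naming only AF, but its burden is "the total number of seconds in clinically significant AF divided by the total Holter recording time in seconds".

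**Rate.** Both documents then say "The numerator will include all subjects in the denominator that meet all four 6-month effectiveness conditions".

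**Recording length.** For recordings longer than 48 hours, Protocol 12.3.1.5 says "the AF burden will be computed by the core laboratory for the initial 48 hours only". For shorter ones it bases AF burden on the usable or analyzable period, and it treats fewer than 24 usable hours as missing unless the subject has already failed on another criterion. The visible text of SAP 3.3.1.3 and 3.3.1.4 shows neither the 48-hour rule nor the 24-hour rule.

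**The concern.** There are two separate mismatches.

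The first lies within each document: the definition covers AF and flutter, while the sentences that produce the result mention AF only. A programmer or core laboratory working from the formula could leave flutter out of the 6-month burden. Protocol 12.3.1.2 says the endpoint is there to show that investigators were not too cautious during the procedure. An omission that can only add successes would work against that purpose.

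The second lies between the documents. Dividing by total time counts unanalyzable time as free of AF. At 6 months this flatters the subject; at baseline it lowers the reference burden and works against the subject. The same recordings can therefore pass under one document and fail under the other.

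What is at stake is the reproducibility of one reported effectiveness rate.

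**Working it through.** **The plan's own figure.** Protocol 12.3.1.6 and SAP 3.3.1.5 assume 200 evaluable subjects and a 55% rate, and state an exact 95% interval no wider than 14.2% with a lower limit of at least 47.8%. Clopper-Pearson for 110/200 gives 47.8% to 62.0%, width 14.2. The figure reproduces and does not depend on this point.

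**Formula.** Reduction = 1 − (6-month burden ÷ baseline burden), with success at 90% or more. Inclusion criterion 1 requires continuous AF on the baseline monitor, so baseline burden is taken as 100% of analyzable time.

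**AF alone versus AF/AFL.** Illustrative 48-hour recordings, fully analyzable, all episodes over 10 minutes:

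| 6-month recording | AF only | AF/AFL |
|---|---|---|
| 0 h AF, 6 h AFL | 1 − 0/48 = 100% (pass) | 1 − 6/48 = 87.5% (fail) |
| 4 h AF, 1 h AFL | 1 − 4/48 = 91.7% (pass) | 1 − 5/48 = 89.6% (fail) |
| 0 h AF, 4 h AFL | 100% (pass) | 1 − 4/48 = 91.7% (pass) |

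With an all-AF baseline, the AF-only residual can never exceed the AF/AFL residual, so the literal formula can only add successes. Without that condition the direction can reverse. With a baseline of 50% AF and 50% AFL, and 6% AF and no AFL at 6 months, AF-only gives 1 − 6/50 = 88% (fail) and AF/AFL gives 1 − 6/100 = 94% (pass).

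**Total versus analyzable time.** Let f0 and f6 be analyzable ÷ total time at baseline and 6 months, and let r be the protocol's residual (6-month burden ÷ baseline burden on analyzable time). Each SAP burden is the protocol burden times its own fraction, so the SAP residual is r × f6/f0. The documents disagree only when r lies between 0.10 and 0.10 × f0/f6.

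- Both recordings at least 90% analyzable (assumed): f0/f6 runs from 0.90 to 1.11, so r at issue runs from 0.09 to 0.111. That is a protocol reduction of 88.9% to just under 91%.
- Both 48-hour recordings with at least 24 h analyzable: f0/f6 runs from 0.5 to 2, so r at issue runs from 0.05 to 0.20. That is 80% to just under 95%. The extremes need one recording half analyzable and the other complete.

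Examples (all with baseline analyzable time wholly AF):

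| Case | Protocol | SAP |
|---|---|---|
| Baseline complete; 6 months 90% analyzable, AF in 11% of analyzable time | 1 − 0.11 = 89.0% (fail) | 1 − 0.11 × 0.9 = 90.1% (pass) |
| Baseline complete; 6 months 30 of 48 h analyzable, 4 h AF | 1 − 4/30 = 86.7% (fail) | 1 − 4/48 = 91.7% (pass) |
| Baseline 24 of 48 h analyzable; 6 months complete, 4 h AF | 1 − (4/48)/(24/24) = 91.7% (pass) | 1 − (4/48)/(24/48) = 83.3% (fail) |
| Both 30 of 48 h analyzable, 4 h AF at 6 months | 1 − 4/30 = 86.7% (fail) | 1 − (4/48)/(30/48) = 86.7% (fail) |

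A 6-month recording that simply stopped at 30 h has total equal to analyzable time, so both documents give 86.7%. Within these ranges, a subject with no AF at 6 months, or still in continuous AF, is classed the same by both.

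**Effect on the rate.** One subject is 1/200 = 0.5 points. Moving one success to failure takes 110/200 = 55.0% to 109/200 = 54.5% (exact 95% CI 47.3% to 61.5%). The documents give neither a flutter frequency nor a distribution of analyzable time. For a purely assumed range of 1 to 10 subjects reclassified as failures, the rate falls to between 54.5% and 50.0% (100/200; CI 42.9% to 57.1%).

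**The case against.** **AF is shorthand.** Clinically significant is defined once in each document, for AF/AFL, and the numerator sentence sends the reader back to the four defined conditions. The protocol shortens the term elsewhere: reablation requires recurrent AF/AFL in 7.15, while 12.3.2.4 speaks only of recurrent AF. This is probably what was meant. It does not settle the matter: the formula has its own parenthetical naming AF over 10 minutes, the pass rule repeats AF alone, and no visible sentence says that AF includes flutter there.

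**The SAP is merely out of date.** SAP version 2 says it is aligned with version 5 of the investigational plan. It keeps 350 subjects, 40 centers and 275 completers against 420, 55 and 284 in the protocol, and speaks only of Holters where Protocol 7.7 also allows patch monitors. That likely explains the denominator, but the conflicting sentence is still in the SAP that governs the PMA and final reports.

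**One core laboratory applies one convention.** That supports consistency across subjects. It does not show which convention the laboratory uses.

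**Stronger readings.** A reader might infer that the plan deliberately ignores flutter, that effectiveness will be materially inflated, or that some particular number of subjects will be misclassified. The documents support none of these. A reader might also infer that the SAP has no 48-hour or 24-hour rule. That cannot be established: part of SAP 3.3.1.3 is redacted, and the available text runs from Table 1 in 2.4 into the middle of the baseline summary, so 2.5 and most of 3.1.1 are not shown. The visible SAP does require 48-hour recordings readable by the core laboratory, and a first-48-hours rule has little to act on with a 48-hour Holter.

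**Conclusion.** The point stands as a minor one. In both documents the scoring text is narrower than the definition it serves, and the SAP and protocol use different denominators. Followed literally, either mismatch can misclassify a subject. The flutter omission can only raise the success rate, given an all-AF baseline. The denominator difference can go either way, and needs both unequal analyzable fractions and a reduction near 90%; the narrow window of about 89% to 91% rests on the assumption that both recordings are at least 90% analyzable.

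No count of affected subjects can be given. Half a point per subject is small against a 14.2-point interval. Protocol 12.3.1.2 sets no hypothesis for this objective, and study success depends only on the stroke endpoint, which none of this touches.

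**What to change.** - **Protocol 12.3.1.4 and SAP 3.3.1.3:** write AF/AFL in the burden formula (including its parenthetical), the percent-reduction sentence and the 90% rule.
- **Protocol 12.3.1.5:** write AF/AFL burden at both places. The protocol denominator needs no change.
- **SAP 3.3.1.3:** make the denominator total analyzable recording time for both the baseline and the 6-month recordings.
- **SAP 3.3.1 throughout:** replace Holter with ambulatory ECG monitor, so that rules written for patch monitors fit the text.
- **SAP 3.3.1.4:** unless redacted or unshown text already has them, carry over the protocol's rules that only the first 48 hours count and that fewer than 24 usable hours is missing, keeping the exception for failure on another criterion.

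The cost is wording, plus confirmation that the core laboratory reports flutter episode durations. It should be done before scoring. The reported effectiveness rate may come out slightly lower.

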12.3.1.6 Confidence Interval Width

The 6-month effectiveness rate among all 138 subjects randomized to the ablation management arm in TTOP-AF was 55.8% (77/138; 95% CI: 47.1% - 64.2%). However, in this intention-to-treat analysis, 17 subjects missing their 6-month ambulatory ECG monitor assessment were included in the analysis as failures. If only subjects with 6-month ambulatory ECG monitor data available in TTOP-AF were included in the analysis (the analogous analysis cohort in this study) the 6-month effectiveness rate was 63.6% (77/121; 95% CI: 54.4% - 72.2%). However, the TTOP-AF protocol required amiodarone be discontinued 28 days prior to the 6-month visit, did not require discontinuation of other antiarrhythmic drugs or DC cardioversions until 5 days prior to the 6-month ambulatory ECG monitor assessment. Thus, while it is expected that the estimated 6-month effectiveness rate in this study will be greater than 50%, it may be less than 64% due to differences in allowed concomitant therapy use between studies.

Based on the following assumptions:

- Up to 420 subjects will be enrolled
- 300 subjects are required to complete the 30-day post-ablation visit and have the opportunity for a reablation procedure (i.e. complete 6-month visit)

or complete the 30-day post-reablation visit if a reablation procedure is required

- Total of 55 study centers activated
- 14 months to activate the 55 centers
- Enrollment rate of 0.4 subjects per center per month once activated
- 30% of subjects will be re-ablated prior to their 6-month visit
- 10% annualized attrition rate

It was estimated via a simulation study that approximately 284 subjects would complete the 6-month ambulatory ECG monitor assessment. Assuming 200 subjects have evaluable baseline and 6-month ambulatory ECG monitor data and the observed 6-month effectiveness rate is 55%, then the exact 95% two-sided confidence interval should have a width no larger than 14.2% with a lower limit of at least 47.8%. Similarly, if the observed 6-month effectiveness rate is 50%, the confidence interval width should be no greater than 14.3% with a lower limit of at least 42.9%.

12.3.1.7 **Missing data**

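### Six-month effectiveness counts subjects without an ECG only when they have already failed, so the rate cannot exceed the both-ECG rate, and the 63.6% TTOP-AF cohort is not its analogue

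*Protocol*

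**What the plan says.** Protocol 12.3.1.4 puts in the denominator ablated subjects who have baseline and 6-month recordings, "or do not have ambulatory ECG data available but were 6-month effectiveness failures based on other criteria". For the numerator it says: "The numerator will include all subjects in the denominator that meet all four 6-month effectiveness conditions". One of those four conditions is the reduction measured on the ECG. Protocol 12.3.1.5 repeats the rule for the analysis set ("or are 6-month effectiveness failures based on other criteria will be included in the main analysis cohort for this objective") and treats a recording with under 24 usable hours as missing. SAP 3.3.1.3 has the same rule, admitting subjects who "do not have Holter data available but were 6-month effectiveness failures based on other criteria", and SAP 3.3.1.4 repeats it.

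Protocol 12.3.1.6 and SAP 3.3.1.5 give two rates from TTOP-AF. The first is 77/138 = 55.8%, in which "17 subjects missing their 6-month ambulatory ECG monitor assessment were included in the analysis as failures" (Protocol wording). The second is 77/121 = 63.6%, restricted to subjects with 6-month ECG data and described as "the analogous analysis cohort in this study". Both sections expect a result above 50% and possibly below 64%. The only reason they give for a shortfall is the difference in concomitant therapy rules.

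Protocol 12.3.1.7 and SAP 3.3.1.6 plan a tipping point analysis. Subjects who complete the 6-month visit without an ECG, and have not failed otherwise, are counted first as successes and then step by step as failures.

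**The concern.** For a subject without an ECG, entry to the denominator depends on outcome. A known failure is counted and a possible success is dropped. This lowers the reported rate for a reason unrelated to how well the procedure worked.

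The benchmark was built on a different rule, because it drops every subject without an ECG, known failures included. Protocol 12.3.1.2 says the main purpose of this objective is to show that operators were not over-cautious. A reader who sets the study's rate beside 63.6% would be comparing two different denominators. The documents would lead that reader to put the whole gap down to drug and cardioversion rules.

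**Working it through.** **Step 1: reproduce the plan's figures** (exact two-sided 95% intervals).
- 77/138 = 55.8% (47.1 to 64.2) and 77/121 = 63.6% (54.4 to 72.2), as stated.
- 138 − 17 = 121, so the 63.6% cohort leaves out all 17 subjects without ECG data.
- Planned precision: 110/200 gives 47.8 to 62.0 (width 14.2) and 100/200 gives 42.9 to 57.1 (width 14.3), as stated.

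**Step 2: direction.** Let E be the number of subjects with both ECGs, S the successes among them, and F the subjects without an ECG who failed on another criterion. The main rate is S/(E + F) and the both-ECG rate is S/E. So the main rate never exceeds the both-ECG rate, and it is lower whenever F is at least 1. This needs no assumption about why ECGs are missing.

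**Step 3: size if ECGs are missing completely at random.** Let p be the true success rate, m the share without an ECG, and f the share of those who fail on another criterion. The expected main rate is

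R = (1 − m)p / [(1 − m) + m·f].

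The documents give no m or f for this study, so these values are assumptions: p = 55%, and f = 10% to 30% (70% to 90% passing the other criteria).

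| m | R at f = 10% | R at f = 30% | Shift, points |
|---|---|---|---|
| 5% | 0.5225/0.955 = 54.7% | 0.5225/0.965 = 54.1% | −0.3 to −0.9 |
| 10% | 0.495/0.91 = 54.4% | 0.495/0.93 = 53.2% | −0.6 to −1.8 |
| 20% | 0.44/0.82 = 53.7% | 0.44/0.86 = 51.2% | −1.3 to −3.8 |

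At TTOP-AF's own level of missing data (m = 17/138 = 12.3%) with p = 63.6%, R is 62.7%, 61.9% and 61.0% for f = 10%, 20% and 30%. The shift is −0.9 to −2.6 points.

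**Step 4: when missingness is not random.** Let q be the true success rate among subjects without an ECG. The main rate is unbiased for all ablated subjects when q = R(1 − f). With m = 12.3%, p = 63.6% among those with an ECG, and f = 20%, that gives q = 0.619 × 0.8 = 49.5%. If q is below this, the main rate overstates the true rate.

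**Step 5: the benchmark on this study's rule.** If k of the 17 TTOP-AF subjects without an ECG failed on another criterion, the comparable rate is 77/(121 + k). The documents do not give k.

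| k | Rate | Exact 95% CI |
|---|---|---|
| 0 | 63.6% | 54.4 to 72.2 |
| 4 | 61.6% | 52.5 to 70.2 |
| 8 | 59.7% | 50.7 to 68.2 |
| 12 | 57.9% | 49.0 to 66.4 |
| 17 | 55.8% | 47.1 to 64.2 |

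The two cohorts give the same figure only if k = 0.

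**Step 6: what the tipping point analysis covers.** It brackets every possible result for undetermined subjects who complete the 6-month visit. It does not reach subjects who exit earlier. An early exit already known to be a failure, such as an acute procedural failure, can enter the main denominator. An early exit with no known failure appears in neither analysis.

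**The case against.** The strongest defence is that counting an established failure of a four-part endpoint is a reasonable, conservative convention, and that the tipping point analysis addresses the group left out. For subjects who complete the 6-month visit this stands. It leaves early exits uncovered, and the planned analyses do not include the both-ECG rate.

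The shift is also small against a planned interval width of 14.2 points, and the objective has no hypothesis. Both facts stand, and they make this a minor point.

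Three stronger readings are tempting, and the documents do not support them:
- **The reported rate is simply too low.** This is certain only relative to the rate in subjects with both ECGs. Relative to the true rate in all ablated subjects it holds under random missingness, and it can vanish or reverse if missing ECGs track recurrence (step 4).
- **The study will be tested against 63.6%.** No test, margin or formal comparison is specified. The figure appears in a section on interval width, where precision is worked at 55% and 50%.
- **TTOP-AF is the only yardstick for over-caution.** Protocol 12.3.1.2 states that purpose but names no benchmark, and acute procedural success is a separate objective that also bears on it.

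It is fair to add that both TTOP-AF rates are already printed side by side, that the differing drug and cardioversion rules are disclosed, and that k could be zero. The comparison would stay imperfect after any correction. None of this makes the analogous label right, because the two inclusion rules differ as written.

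**Conclusion.** The concern holds in a limited form. Inclusion of subjects without an ECG depends on outcome, so the main rate is at most the both-ECG rate and usually below it. The size in step 3, from 0.3 to 3.8 points across 5% to 20% missing, rests on random missingness, a true rate of 55% and a 70% to 90% pass share on the other criteria. All of these are assumptions.

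The benchmark statement in Protocol 12.3.1.6 and SAP 3.3.1.5 is wrong as worded. The figure on this study's rule is known only to lie between 55.8% and 63.6%. The study's success decision does not turn on this objective, so the change is worth making but not critical.

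**What to change.** 1. Keep the main rate and the tipping point analysis as planned.
2. In Protocol 12.3.1.4 and SAP 3.3.1.3, add one reported line: the success rate with an exact 95% interval in subjects whose baseline and 6-month ECGs are both readable. This is the true analogue of 77/121.
3. In Protocol 12.3.1.6 and SAP 3.3.1.5, replace the analogous label with a statement that the TTOP-AF figure on this study's rule lies between 55.8% and 63.6%. Name the denominator rule, alongside concomitant therapy, as a reason the result may fall below 64%.

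The cost is one table line from data already collected, a short text change in each document, and a slightly less favourable benchmark.

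An estimate that multiplies the share passing the non-ECG criteria by the ECG success share among those who pass is not recommended. The drug and cardioversion criteria are timed back from an ECG that these subjects lack. Early exits can be known failures but not known passes, so the same asymmetry would return.
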